## 5.4. Baseline, Post-Baseline Changes, and LOCF

Unless stated otherwise, baseline and post-baseline change values will be based on the following:

- Baseline will be based on the last non-missing value collected prior to or on the date/time of first dose of study drug.
- Post-baseline values will be those collected after the date/time of first dose of study drug.
- Change from baseline is defined as: value – baseline value.
- Percentage change from baseline is defined as:  $[(\text{value} - \text{baseline value}) / \text{baseline value}] * 100$ . Patients with baseline values of zero are excluded due to division by zero.
- Most extreme change: The maximum most extreme change will be the maximum post-baseline change value; the minimum most extreme change will be the smallest post-baseline change value. This calculation will consider all assessments collected after the first dose of study drug, scheduled or unscheduled.
- LOCF:
  - Imputation rules for assessments that include multiple components:
    - In case of missing laboratory components, lab values from the most recent unscheduled visit  $\leq 14$  days after the nominal visit will be utilized. If lab values are not available from an unscheduled visit  $\leq 14$  days after the visit, laboratory data will be carried forward from the most recent laboratory assessment  $\leq 30$  (scheduled or unscheduled) days prior to the nominal visit.
    - In case of missing non-laboratory components, no imputation will be performed.
  - In case of missing the entire score for an assessment, imputation will be based on LOCF. LOCF will only be implemented with the most recent prior visit (including unscheduled assessments). If the most recent prior visit is missing, occurred more than 30 days before (current visit date – most recent prior visit date  $> 30$ ), or is not evaluable, LOCF is not implemented. See Section 7 for further details. Additional details regarding LOCF for components for specific assessments are described in Section 7.
  - Observed values do not incorporate any imputations and are presented as collected.

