  - Note: Treatment with inhaled CS are allowed for the treatment of non-SLE-related indications only (e.g., for asthma).

Sponsor: Boston Pharmaceuticals, Inc.  
Protocol Number: BOS161721-02  
SAP Version and Date: Version 4.0, 23Apr2021

Any other increase from baseline of CS dose or any other systemic use of CS of any kind (including intra-articular and intravenous administration) are not permitted from Day 0 through Day 210 and will result in the patient being considered a medication failure and will be treated as non-responders for the primary efficacy analysis. There is no restriction of CS usage after Day 210.

The determination of medication failures will be reviewed using blinded data and finalized prior to unblinding. Once a patient is determined to be a non-responder, the patient will remain a non-responder for the remainder of the study.

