| SLEDAI-2K | 
If lab values are missing at Day 210, lab values will be imputed based on the below hierarchy of determination:
 
(1) If any unscheduled laboratory assessments occurred <=14 days after the Day 210 visit, the laboratory values at the most recent unscheduled laboratory assessment will be used for the determination of missing laboratory SLEDAI-2K criteria. For example, if platelet count is missing at Day 210 and an unscheduled laboratory assessment occurs 10 days after the Day 210 visit date, the platelet count from the unscheduled laboratory assessment would be used to determine if the patient had thrombocytopenia at Day 210 for SLEDAI-2K.
 
(2) Else if #1 does not occur or lab values are not available at the unscheduled visit noted in #1, the laboratory data will be carried forward from the most recent laboratory assessment (scheduled or unscheduled) <=30 days prior to the Day 210 nominal visit to make the SLEDAI-2K determination. For example, if a patient is missing thrombocytopenia and leukopenia SLEDAI-2K components at Day 210, they have an unscheduled lab assessment 10 days earlier with platelet counts populated and WBC not populated, and they have a Day 180 assessment within 30 days of the Day 210 visit with both platelets and WBC present, the platelet value from the unscheduled visit would be carried forward to the Day 210 for thrombocytopenia component designation and the WBC value would be carried forward from the Day 180 assessment to Day 210 for the Leukopenia component designation.
 
(3) If the lab components for SLEDAI-2K are missing from Day 210 and no unscheduled laboratory assessments occur within 14 days after or 30 days prior to the Day 210 assessment, the lab components from Day 180 will be carried forward, if available and if Day 180 occurred within 30 days of Day 210.
 
Otherwise, no non-lab individual SLEDAI-2K components will be carried forward. If non-lab individual components are missing at Day 210, the entire SLEDAI-2K score from Day 180 will be carried forward. If Day 180 is missing, occurred more than 30 days before Day 210, or is not
 |

|     |   |
|-----|---|

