| Sensitivity Analysis 1:
Observed (no LOCF for missing data),
Medication Failures=Non-Responder | FAS | 
A sensitivity analysis of the primary efficacy endpoint may be performed based on purely observed data. No LOCF imputations will be performed for missing data.
 
Additional criteria are as follows:
 
 
(1) Medication failures are considered non-responders on and after the date of medication failure
 
(2) Early withdrawals/discontinuations prior to Day 210 will be considered non-responders after the date of early withdrawal/discontinuation 
 
a. If patient is a medication failure prior to withdrawal/discontinuation, patient will be considered a non-responder on and after the date of medication failure.
 
 
 
 
(3) Patients with missing Day 210 data without prior medication failure and without early withdrawal/discontinuation prior to Day 210 are considered not evaluable and are excluded from the sensitivity analysis
 
If lab component scores are carried forward from Day 180 to Day 210 in order to assign a Day 210 grade in the primary analysis, the Day 210 assessment will be considered not evaluable for this sensitivity analysis.
 |
| Sensitivity Analysis 2:
LOCF for missing data,
Exclude Medication Failures                     | FAS | 
A sensitivity analysis of the primary efficacy endpoint may be performed based on LOCF methods for missing data detailed for the primary efficacy analysis.
 
Additional/modified criteria are as follows:
 
 
(1) Medication failures are considered not evaluable and are excluded from the sensitivity analysis on and after the date of medication failure
 
   |

|  |     |  |
|--|-----|--|

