#### 7.2.10. Systemic Lupus Erythematosus Disease Activity Index 2000 (SLEDAI-2K)

The SLEDAI-2K is a validated instrument that measures disease activity in SLE patients at the time of the visit and in the previous 30 days. It is a global index and includes 24 clinical and laboratory variables that are weighted by the type of manifestation, but not by severity. The total score falls between 0 and 105, with higher scores representing increased disease activity. The SLEDAI-2K has been shown to be a valid and reliable disease activity measure in multiple patient groups. A SLEDAI 2K of 6 or more generally represents moderately to severely active disease.

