### 13.3. SLEDAI-2K Index

|   |  |                        |  |
|---|--|------------------------|--|
| Subject Number: _____ - _____   |  |                        | Protocol BOS161721-02  |
| Screening / Randomization / _____ Week Visit & Date of Assessment: _____ - _____ - 20
(Circle visit type &/or enter visit week)                          |  |                        | (Day) _____ Month _____ Year _____   |
| SLEDAI 2K Index
Must be present at the time of visit or in the preceding 30 days (or 10 days for V1 and V2) and SLE-Related to be checked! |  |                        |  |
| Wt  | (  ) if Present | Descriptor             | Definitions
If descriptor is checked as present, please check appropriate condition(s) in definition and/or specify in the space provided.   |
| 8   |                            | Seizure                | Recent onset (last 28 days). Exclude metabolic, infectious or drug causes. Specify if checked:  |
| 8   |                            | Psychosis              | Altered ability to function in normal activity due to severe disturbance in the perception of reality. Include:  hallucinations,  incoherence,  marked loose associations,  impoverished thought content,  marked illogical thinking, and  bizarre, disorganized, or catatonic behavior. Exclude uremia and drug causes.   |
| 8   |                            | Organic Brain Syndrome | Altered mental function with  impaired orientation, memory or other intellectual function (with rapid onset and fluctuating clinical features),  inability to sustain attention to environment, and at least 2 of the following:  perceptual disturbance,  incoherent speech,  insomnia or daytime drowsiness,  increased or decreased psychomotor activity. Exclude metabolic, infectious or drug causes. |

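### A missing Day 210 laboratory item may be filled from a draw taken after treatment was changed following the endpoint visit, and this can create an SRI-4 response

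*SAP*

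**What the plan says.** All references are to SAP version 4.0.

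- **Section 5.4** gives the general rule: "In case of missing laboratory components, lab values from the most recent unscheduled visit" within 14 days after the nominal visit come first. A draw from the 30 days before the visit is the fallback.
- **Table 1, SLEDAI-2K row**, repeats the order for Day 210. In step 1, "the laboratory values at the most recent unscheduled laboratory assessment will be used for the determination of missing laboratory SLEDAI-2K criteria". Its example is a missing platelet count: if "an unscheduled laboratory assessment occurs 10 days after the Day 210 visit date, the platelet count from the unscheduled laboratory assessment would be used". Step 2, the look-back draw, opens "Else if #1 does not occur or lab values are not available at the unscheduled visit noted in #1". The BILAG row uses the same order.
- **Section 7.1.1, Medication Failures**, says: "There is no restriction of CS usage after Day 210". Disallowed CS use counts from Day 0 through Day 210, and failure status applies from its own date onward.
- **Section 7.2.10** says that the SLEDAI-2K "measures disease activity in SLE patients at the time of the visit and in the previous 30 days". The form in Appendix 13.3 agrees: "Must be present at the time of visit or in the preceding 30 days".
- **Table 2** describes Sensitivity Analyses 1 and 3 as "based on purely observed data. No LOCF imputations will be performed for missing data". Each adds one sentence making Day 210 not evaluable when a laboratory score was carried forward from Day 180. Neither mentions a value carried back from after Day 210.

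**The concern.** The index looks back from the visit, but the imputation rule looks forward first. A draw 14 days after Day 210 outranks one taken the day before it. In those 14 days the investigator may start or raise CS with no consequence for the Day 210 result, and nothing in the rule asks whether that happened. The primary endpoint could then record the effect of treatment given after the endpoint visit as a response to study drug or placebo. Read literally, the words most recent also select the last of several post-visit draws, which is the one with most time for new treatment to act.

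**Working it through.** The SAP states no figure on this point, so there is none to reproduce. The check sets the rules side by side and asks when one item decides the response.

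**1. Does any rule exclude the draw?** Suppose CS is raised on Day 211 and an unscheduled laboratory assessment follows on Day 223.
- The draw is 13 days after Day 210, so step 1 of Table 1 applies.
- The increase falls outside Day 0 through Day 210, so it is not a medication failure.
- A prohibited drug started on Day 211 would give failure status from Day 211 on, which leaves Day 210 unchanged.
- A Day 200 draw lies inside the look-back window, but step 2 is never reached.
- The one check in the SLEDAI-2K row is blinded clinical input, which is optional and has no stated criterion.

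So the Day 223 value is scored as Day 210.

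**2. Weight of the laboratory items (Appendix 13.3).** Four urinary items at 4, complement and DNA binding at 2 each, platelets and leukocytes at 1 each: 4×4 + 2×2 + 2×1 = 22. The form total is 8×8 + 6×4 + 7×2 + 3×1 = 105, which agrees with the range in Section 7.2.10.

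**3. When does one item decide the 4-point criterion?** Let w be the weight of an item present at baseline and r the fall on all other items. If the item is scored absent at Day 210 the total fall is r + w; if present, it is r. The item decides when r < 4 ≤ r + w, that is, when 4 − w ≤ r ≤ 3.

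| Item | w | Decides when r is |
|---|---|---|
| Casts, hematuria, proteinuria, pyuria | 4 | 0 to 3 |
| Low complement, DNA binding | 2 | 2 to 3 |
| Platelets, leukocytes | 1 | 3 only |

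Illustration: proteinuria at baseline and on Day 200, urine missing on Day 210, CS raised on Day 211, clear urine on Day 223, nothing else changed (r = 0). The plan scores a 4-point fall. The look-back draw would score 0. That the urine clears in this time is assumed for illustration.

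**4. Effect of one patient.** The 96 evaluable patients at 2:1 give 64 and 32. One patient is 1/64 = 1.6 or 1/32 = 3.1 percentage points. Uncorrected Pearson chi-square, N(ad − bc)²/(product of the four margins), with 10/32 placebo responders:
- 31/64 active: 96 × (31×22 − 33×10)² / (64×32×41×55) = 2.576, p = 0.1085.
- 32/64 active: 96 × (32×22 − 32×10)² / (64×32×42×54) = 3.048, p = 0.0809.

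One patient can cross the 0.10 level, but only if the result is already near it.

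**5. Sensitivity Analyses 1 and 3.** For SLEDAI-2K, Section 5.4 lists the post-visit rule as an imputation under LOCF and says that observed values contain no imputations. Table 1 also calls the filled values imputed. Together with Table 2, this keeps such values out of the observed SLEDAI-2K score. For BILAG, Table 1 has the medical monitoring team set the grade with the substituted value and enter it in the clinical database. No flag is required, so an observed-data analysis cannot tell such a grade from an observed one.

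**The case against.** **A prompt redraw is often the better measurement.** A Day 211 redraw with no treatment change is closer to the endpoint than a Day 180 value up to 30 days old. This stands. A reader might infer that the order should simply be reversed. The documents do not support that: Day 180 is a scheduled visit and would often displace a redraw one day late. The defect is the missing condition on treatment, not the order as such.

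**Both observed-data analyses keep the later values.** A reader might infer this from the Day 180 sentence. For SLEDAI-2K it does not hold, as step 5 shows. It stands only for BILAG grades.

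**Post-visit treatment could also remove a response.** The arithmetic allows an item absent at baseline to undo a response when other items have fallen by 4 to 7 points (w = 4). But that needs new activity to appear after the visit, and the SAP shows no route by which added treatment would produce it.

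**The case is rare, and there are checks.** It needs a missing Day 210 item, an unscheduled draw within 14 days, a treatment change in between, a changed item state and a patient near the threshold. The platelet item in Table 1's example decides only when r = 3. BILAG grades are adjudicated, disease-activity data are centrally reviewed, and clinical input may be sought for values carried back. The rarity stands. The checks help, but none has a stated criterion on treatment after Day 210. Missing central results are plausible, because Appendix 13.1 keeps local laboratory results obtained during courier disruption out of the database.

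**Conclusion.** The point holds in a limited form and should be corrected. The rules allow a laboratory value altered by treatment begun after Day 210 to be scored as Day 210, outside the instrument's own look-back window, and so to create an SRI-4 response in the primary analysis. Urinary items carry the case, since one of them can meet the SLEDAI-2K threshold alone.

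The size cannot be computed. The SAP gives no frequency of missing items, unscheduled draws or treatment changes, so any percentage would be a guess. The number of patients is probably small, at 1.6 or 3.1 percentage points each if the evaluable numbers are 64 and 32. No direction of bias between arms follows from the documents. Sample size, significance level and power are unaffected.

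**What to change.** Data handling only; the CS rules stay as they are.

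1. In Section 5.4 and in the BILAG and SLEDAI-2K rows of Table 1, do not use a post-visit draw if any systemic CS or protocol-prohibited medication was started or increased between the Day 210 visit and the draw. Take the dates from the concomitant medication eCRF, which Table 4 already uses to date medication failure. Go to the look-back draw instead.
2. Where more than one post-visit draw is eligible, use the one closest to Day 210 in place of the most recent.
3. In Sensitivity Analyses 1 and 3, extend the Day 180 laboratory sentence to values carried back from after Day 210. Flag each BILAG grade set with a substituted laboratory value, and treat it as not evaluable in those analyses.

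The cost is a wording change, a derivation edit and a BILAG flag, with a few more look-back or not-evaluable values. A redraw shortly after Day 210 keeps its priority when treatment has not changed. The edit must be final before unblinding.

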**Table 2**

| Analysis   | Analysis Population | Criteria   |
|--|---------------------|--|
| Primary Analysis

LOCF for missing data,
Medication
Failures=Non-Responder | FAS                 | 
The primary analysis of the primary efficacy endpoint will be performed based on LOCF methods for missing data.
 
 
(1) Medication failures are considered non-responders on and after the date of medication failure
 
(2) Early withdrawals/discontinuations prior to study day 159 will be considered non-responders after the date of early withdrawal/discontinuation
 
 |

|  |     |  |
|--|-----|--|
|  |     | 
 
a. If patient is a medication failure prior to withdrawal/discontinuation, patient will be considered a non-responder on and after the date of medication failure.
 
b. In case of early withdrawal/discontinuation after study day 159 but before Day 210 such that patient has Day 180 data but is lacking Day 210 data in a patient without medication failure, the Day 180 data will be carried forward to Day 210.
 
 
(3) Patients with missing Day 180 and Day 210 data without prior medication failure and without early withdrawal/discontinuation prior to study day 159 are considered not evaluable and are excluded from analysis
  |
| Sensitivity Analysis 1:
Observed (no LOCF for missing data),
Medication Failures=Non-Responder | FAS | 
A sensitivity analysis of the primary efficacy endpoint may be performed based on purely observed data. No LOCF imputations will be performed for missing data.
 
Additional criteria are as follows:
 
 
(1) Medication failures are considered non-responders on and after the date of medication failure
 
(2) Early withdrawals/discontinuations prior to Day 210 will be considered non-responders after the date of early withdrawal/discontinuation 
 
a. If patient is a medication failure prior to withdrawal/discontinuation, patient will be considered a non-responder on and after the date of medication failure.
 
 
 
 
(3) Patients with missing Day 210 data without prior medication failure and without early withdrawal/discontinuation prior to Day 210 are considered not evaluable and are excluded from the sensitivity analysis
 
If lab component scores are carried forward from Day 180 to Day 210 in order to assign a Day 210 grade in the primary analysis, the Day 210 assessment will be considered not evaluable for this sensitivity analysis.
 |
| Sensitivity Analysis 2:
LOCF for missing data,
Exclude Medication Failures                     | FAS | 
A sensitivity analysis of the primary efficacy endpoint may be performed based on LOCF methods for missing data detailed for the primary efficacy analysis.
 
Additional/modified criteria are as follows:
 
 
(1) Medication failures are considered not evaluable and are excluded from the sensitivity analysis on and after the date of medication failure
 
   |

|  |     |  |
|--|-----|--|
|  |     | 
(2) Early withdrawals/discontinuations prior to study day 159 will be considered not evaluable and will be excluded from analysis after the date of early withdrawal/discontinuation
 
 
a. If patient is a medication failure prior to withdrawal/discontinuation, patient will be considered not evaluable and excluded on and after the date of medication failure.
 
b. In case of early withdrawal/discontinuation after study day 159 but before Day 210 such that patient has Day 180 data but is lacking Day 210 data in a patient without medication failure, the Day 180 data will be carried forward to Day 210.
 
 
(3) Patients with missing Day 180 and Day 210 data are considered not evaluable and are excluded from the sensitivity analysis
  |
| Sensitivity Analysis 3:
Observed (no LOCF for missing data), Exclude Medication Failures                        | FAS | 
A sensitivity analysis of the primary efficacy endpoint may be performed based on purely observed data. No LOCF imputations will be performed for missing data.
 
Additional criteria are as follows:
 
 
(1) Medication failures are considered not evaluable and are excluded from the sensitivity analysis on and after the date of medication failure
 
(2) Early withdrawals/discontinuations prior to Day 210 will be considered not evaluable and are excluded from the sensitivity analysis after the date of early withdrawal/discontinuation
 
a. If patient is a medication failure prior to withdrawal/discontinuation, patient will be considered not evaluable and excluded on and after the date of medication failure.
 
 
(3) Patients with missing Day 210 data are considered not evaluable and are excluded from the sensitivity analysis
 
If lab component scores are carried forward from Day 180 to Day 210 in order to assign a Day 210 grade in the primary analysis, the Day 210 assessment will be considered not evaluable for this sensitivity analysis.
 |
| Sensitivity Analysis 4:
LOCF for missing data,
Medication Failures=Non-
Responder, Logistic
Regression | FAS | 
CCI
 
[REDACTED]
 
[REDACTED]
 
[REDACTED]
   |

Sponsor: Boston Pharmaceuticals, Inc.  
Protocol Number: BOS161721-02  
SAP Version and Date: Version 4.0, 23Apr2021

Additional sensitivity analyses may be performed to consider the effect of missing data.

Statistical testing data will be omitted from MAD Phase 1b treatment group displays.

A summary of disposition of SRI-4 response per the primary analysis at day 210 will be presented by study phase and treatment group in the FAS and PP. Sensitivity analysis 2 (LOCF, Exclude Medication Failures) will also be performed for disposition of SRI-4 response at day 210. These summaries will include the number of SRI-4 responders and the number of SRI-4 non-responders with a breakdown of reasons for non-response (early withdrawal, medication failure, <4-point reduction from baseline in SLEDAI-2K total score, new BILAG 1A/2B, and PGA worsening). Denominators for percentages will be the number of patients eligible for SRI-4 response analysis (patients not deemed not evaluable) defined as those with data for PGA, SLEDAI-2K and BILAG at Day 210 (whether or not due to LOCF, FAS analysis).

A listing of SRI Response data at Days 30, 60, 90, 120, 150, 180 and 210 will be presented in the FAS. A listing of SRI-4 Response at Day 210 (Primary and Sensitivity Analyses) will also be presented in the FAS. A listing of patients with medication failures, early withdrawals/discontinuations and those excluded from the primary efficacy analysis will also be provided for all randomized patients.

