**Table 1**

| SRI-4 Component | Method for Carrying Forward Individual Items Contributing to SRI-4 Component Result/Score  |
|------------------------|---|
| BILAG Grade            | BILAG Grading is evaluated and entered into the clinical database by the medical monitoring team. Grades are adjudicated by independent subject matter experts. The medical monitoring team and the adjudication team will utilize BILAG index results to determine BILAG Grades. Missing data will be handled by the medical monitoring team as follows. If lab values are missing in the BILAG Index at Day 210, lab values from the most recent unscheduled visit $\leq$ 14 days after Day 210 will be utilized for determination of the BILAG grade in the applicable organ system and entered into the clinical database. If lab values are not available from an unscheduled visit $\leq$ 14 days after Day 210, laboratory data will be carried forward from the most recent laboratory assessment (scheduled or unscheduled) $\leq$ 30 days prior to the Day 210 nominal visit for determination of BILAG grade. If the lab components for BILAG are missing from Day 210 and no unscheduled laboratory assessments occur within 14 days after or 30 days prior to the Day 210 assessment, the lab components from Day 180 will be utilized if Day 180 occurred within 30 days of Day 210. Otherwise, no individual BILAG Index results will be carried forward. If the BILAG grade for a given organ system is missing at Day 210, the grade will be carried forward from the Day 180 assessment. If the Day 180 BILAG grade is also missing, occurred more than 30 days before Day 210 (Day 210 visit date – Day 180 visit date > |

Sponsor: Boston Pharmaceuticals, Inc.

Protocol Number: BOS161721-02

SAP Version and Date: Version 4.0, 23Apr2021

|           |   |
|-----------|---|
|           | 30), or is not evaluable, the Day 210 grade will be considered not evaluable.   |

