|     | 
evaluable, LOCF is not implemented and the Day 210 score will be considered not evaluable. In the case of missing SLEDAI-2K lab components at Day 210, where any SLEDAI-2K lab component is carried forward (or back) per above, the SLEDAI-2K total score will be recalculated outside of the clinical database as the sum of:
 
 
(1) All of the non-missing weights for each descriptor at Day 210
 
(2) All individual lab component weights carried forward from the Day 180 visit or unscheduled visit, as applicable.
 
 
If any components are still missing at Day 210 after carrying forward available lab components, the Day 210 SLEDAI-2K score will not be recalculated and will be considered not evaluable.
 
Note: Clinical input may be obtained prior to database lock and unblinding to make a final determination of SLEDAI-2K criteria in the case of carrying forward (or back) individual lab component scores.
 |
| PGA | 
Individual components are not applicable for PGA and will not be carried forward. Total PGA VAS measurement will be carried forward from the Day 180 visit in the case of missing PGA measurement at Day 210. If total PGA score is also missing from Day 180, occurred more than 30 days before Day 210, or is not evaluable, LOCF is not implemented and the Day 210 visit will be considered not evaluable.
   |

Table 2 summarizes the primary analysis and details several sensitivity analyses which may be performed:

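### Sensitivity Analyses 1 and 3 are labelled as observed data but remove only labs carried from Day 180, so Day 210 BILAG grades set with unscheduled labs stay in

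*SAP*

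**What the plan says.** SAP Version 4.0, Section 7.1.1, Table 2 describes Sensitivity Analyses 1 and 3 in the same terms: each "may be performed based on purely observed data. No LOCF imputations will be performed for missing data". Both rows end with the same laboratory exclusion. It begins "If lab component scores are carried forward from Day 180 to Day 210 in order to assign a Day 210 grade" and makes the Day 210 assessment not evaluable for that analysis. Day 180 is the only source it names.

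Section 5.4 gives the general rule: "Observed values do not incorporate any imputations and are presented as collected". The same section lists the rules for replacing missing labs under its LOCF bullet.

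Table 1 sets out the replacement for each SRI-4 component.

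- **SLEDAI-2K.** If there is an unscheduled lab within 14 days after Day 210, "the laboratory values at the most recent unscheduled laboratory assessment will be used for the determination of missing laboratory SLEDAI-2K criteria". Failing that, the latest lab within the 30 days before Day 210 is used, whether scheduled or not. Day 180 is listed last. When a substitute is used, "the SLEDAI-2K total score will be recalculated outside of the clinical database as the sum of" the available and substituted weights.
- **BILAG.** The order of sources is the same, but the substitution is made by the medical monitoring team. Labs from an unscheduled visit within 14 days after Day 210 "will be utilized for determination of the BILAG grade in the applicable organ system and entered into the clinical database".

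**The concern.** Of the four sensitivity analyses listed in Table 2, only 1 and 3 are run without LOCF. They are therefore the only ones that show whether the SRI-4 result depends on carried data. If substituted lab data remain in them, part of any agreement with the primary analysis is built in, and the observed-data label is not accurate.

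The exclusion sentence covers one of the replacement routes in Table 1 and is silent on unscheduled labs, whether drawn before or after Day 210. The question is whether the SAP's other rules close that gap. They do not for BILAG. For SLEDAI-2K they probably do, though not cleanly.

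**Working it through.** No figure in the plan is in dispute, so the check sets the routes beside the exclusion.

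| Source of the substitute Day 210 lab | Allowed by Table 1 | Named in the exclusion (Analyses 1 and 3) |
|---|---|---|
| Unscheduled visit, up to 14 days after | Yes, first choice | No |
| Unscheduled visit, up to 30 days before | Yes, second choice | No |
| Day 180, within 30 days before | Yes, second or last choice | Yes |

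**Step 1: BILAG.** The substitute enters when the grade is assigned, and the grade is then stored in the clinical database. The programmer receives a Day 210 grade that is not missing. A ban on LOCF has nothing to act on, and presenting the value as collected returns the substituted grade. Only an explicit exclusion can remove it, and the one provided stops at Day 180. Section 7.2.5 shows that the SAP regards such grades as compatible with a no-LOCF analysis: flares are assessed on BILAG grades even where the assessor carried component data forward, while LOCF is ruled out for the flare data itself. For BILAG the gap is real.

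**Step 2: SLEDAI-2K.** A total that uses substitute labs exists only if someone applies Table 1 outside the database. Section 5.4 classes both unscheduled routes as LOCF imputation rules and says observed values contain no imputations. The better reading is that such totals are already out. Two things blur it. If the general ban were meant to do all the work, the Day 180 sentence would be unnecessary for SLEDAI-2K. And a lab brought back from after Day 210 is not literally a last observation carried forward, so only the Section 5.4 sentence clearly bars it. Elsewhere Table 1 does say forward or back, and Day 180 or unscheduled visit, when it means every source.

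**Step 3: what a substituted item could change.**

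- *BILAG.* The worksheet in Appendix 13.4 records laboratory values in the renal and haematological systems. Under the SRI-4 definition in Section 7.1.1, one new A grade fails the criterion. A single new B grade does not; more than one is needed.
- *SLEDAI-2K* (relevant only to the ambiguity). Weights of the worksheet items marked as lab-based in Appendix 13.3: four urinary items 4 × 4 = 16, complement and anti-DNA 2 × 2 = 4, platelets and white cells 2 × 1 = 2, total 22. The remaining items sum to 64 + 8 + 10 + 1 = 83, and 83 + 22 = 105, the maximum in Section 7.2.10. One urinary item equals the 4-point SRI-4 threshold.

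**Step 4: what the fix could cost in evaluable patients.** Inputs from Section 3.3: 62% versus 33%, 2:1 allocation, two-sided 10% level, 96 evaluable patients, 80% power. The continuity-corrected formula returns N = 96, which reproduces the plan. The uncorrected formula returns N = 81. Pooled chi-square power without correction is

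Φ{[|p1 − p2| − 1.645·√(p̄(1 − p̄)(1/n1 + 1/n2))] / √(p1(1 − p1)/n1 + p2(1 − p2)/n2)}.

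With n1 = 64 and n2 = 32, p̄ = (64 × 0.62 + 32 × 0.33)/96 = 0.523, which gives 86.2%. If 3, 6, 9 or 12 patients became not evaluable, with 2:1 kept, it would be 85.2%, 84.1%, 83.0% or 81.8%. These counts are assumptions. The SAP gives none.

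**The case against.** The strongest reply is that both analyses open with a general ban on LOCF, that Section 5.4 files the unscheduled-lab rules under LOCF, and that the Day 180 sentence adds an exclusion without cancelling the ban. A reader might infer that SLEDAI-2K scores completed with unscheduled labs count as observed. The SAP does not say so, and for SLEDAI-2K this reply stands apart from the ambiguity in Step 2. It does not reach BILAG, where the substitution is already inside the stored grade.

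Second, both analyses are optional, and the sensitivity analysis the SAP commits to for the SRI-4 disposition summary is number 2, which uses LOCF by design. That limits the severity. But Section 7.1.1 also commits to a listing of Day 210 SRI-4 response for the primary and sensitivity analyses, and an analysis that is run should match its label.

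Third, a marker for substituted grades may exist elsewhere. Section 3.1 refers review processes to the Medical Data Review Plan and the BILAG-2004 Review Guidelines, which are not at hand, and the Day 180 exclusion itself presupposes that carried labs can be identified. This is fair: the SAP names no flag, but that does not show there is none.

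Two further inferences should be resisted. One is that labs drawn after Day 210 could reflect new corticosteroid, since "There is no restriction of CS usage after Day 210". That is speculative and bears on the carry-back rule of the primary analysis, not on the wording of these two. The other is a count of affected patients. A patient must lack a Day 210 lab and also have an unscheduled one in the window. Appendix 13.1 foresees courier problems with central labs but keeps the local results out of the database, so it points both ways.

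**Conclusion.** The point holds for BILAG. As written, a Day 210 grade set with an unscheduled lab from up to 14 days after or 30 days before the visit stays in Sensitivity Analyses 1 and 3 as observed. For SLEDAI-2K there is an ambiguity only, sharpest for labs brought back from after Day 210, and the better reading already excludes them.

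The size cannot be calculated from the SAP. The number of affected patients is not given and may be zero. The 22 of 105 SLEDAI-2K points do not measure the BILAG gap. The primary analysis and its test are unaffected, and both sensitivity analyses are optional. Severity is minor. The conclusion assumes that the grade the monitoring team enters is the one the programmer uses, with no marker for substitution applied from another document.

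**What to change.** In the Table 2 rows for Sensitivity Analyses 1 and 3, replace the laboratory sentence with:

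*If any laboratory item used for the Day 210 BILAG grade or SLEDAI-2K score was not collected at the Day 210 nominal visit (carried forward or back, from Day 180 or an unscheduled visit), the Day 210 assessment is treated as not evaluable in this sensitivity analysis.*

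Have every Day 210 BILAG grade set with a substituted lab identified by a flag before unblinding. If the review documents already provide such a flag, a cross-reference is enough.

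The cost is one sentence in two table rows and one blinded data item. The downside is possibly a few more patients without an evaluable outcome in these two analyses; Step 4 suggests that such a loss would cost little precision.
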